Document date: 07/18/2023

Impacts of mitochondrial-targeted antioxidant on leg function, leg blood flow and skeletal muscle mitochondrial function in peripheral artery disease patients: full study protocol and statistical analysis plan

NCT# 03506633

Study protocol

Participants

Patients with PAD (n = 13, 7 males and 6 females) were recruited for study participation. Disease staging, claudication history, and ankle-brachial index of <0.90 were determined by both self-report and by physician diagnosis, and all participants were classified as Fontaine stage IIa and IIb (16). Participants were also required to have a stable BP, lipid, and/or diabetes regimen for \geq 6 wk prior to participation, and all females were postmenopausal (no menses for \geq 12 consecutive months). Participants were excluded from the study if they had a history of pain at rest (Fontaine stage III) and/or tissue loss due to PAD (Fontaine stage IV), limited walking capacity due to conditions other than PAD, or renal disease. Participants were also asked to track what they consumed the day before their first visit so they could consume the same foods prior to their second visit. In addition, participants were requested to not alter their digtary habits during the 2 wk washout period. All procedures were performed according with the protocols approved by the Institutional Review Board and performed in accordance with the Declaration of Helsinki. All participants provided written, informed consent prior to beginning the study. This study was registered with https://clinicaltrials.gov/ (NCT03506633).

Design

This study used a randomized, double-blinded, placebo-controlled, crossover design with a washout period of 14 days between the 2 study visits (**Fig. 1**). Participants were randomly assigned to receive either 80 mg of MitoQ or placebo. In a previous study, MitoQ showed pharmacokinetic behavior at doses of 80 mg (1mg/1kg), resulting in plasma maximal concentration of 33.15 ng.ml, which is safe for humans. Additionally, administration of 20 mg/1kg of mitoQ was shown to have no toxicity in previous research. The dose in this study was considerably lower than this amount. These findings led us to believe the recommended

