80 mg dose is ideal for this study. The PL consisted of tapioca powder capsules that possessed no nitrate or antioxidant properties. Participants were informed that we were researching the effects of commercially available juice and pills on their vascular function and walking capacity; therefore, they were not aware that the capsules were PL. All assessments were performed after an overnight fast and at the same time of day (9:00 AM \pm 1 h). Anthropometric measurements were obtained upon arrival at both visits. Following anthropometrics, baseline experimental measurements were conducted, after which the MitoQ supplement or PL were consumed. All experimental measurements were repeated ~ 1 h following ingestion. All data analyses were performed in a blinded manner.

Anthropometrics

Anthropometric measurements included height, body mass, and body composition. Height was measured using a stadiometer (nearest 0.5 cm). Body mass was measured using a standard scale (nearest 0.1 kg), and body mass index was calculated by taking the body mass divided by height squared (kg/m²). Body fat percentage was assessed using bioelectrical impedance analysis in duplicate to the nearest 0.1% (HBF – 306C, Omron Healthcare, Lake Forest, IL), and the average of the 2 measures was recorded as the body fat percentage.

Resting heart rate and blood pressure

Participants sat for 15 min in a quiet and temperature-controlled room. Resting heart rate and BP were assessed in duplicate using an automated sphygmomanometer (HEM – FL 31, Omron Healthcare, Lake Forest, IL). The two measurements were taken with 5 min separating each measurement, and the average of the 2 was recorded as the resting heart rate and BP.

Endothelial function

Endothelial function was assessed using brachial artery flow-mediated dilation (FMD) and popliteal artery FMD using a Doppler ultrasound (Terason uSmart 3300, Terason Division Teratech Corporation, Burlington, MA), rapid inflation cuff system (E20 Rapid Cuff and cuff model SC5, D.E. Hokanson, Bellevue, WA), and a 3-lead electrocardiogram system (7700 Series

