estimate the change in tissue saturation (StO₂), deoxygenated hemoglobin concentration ([HHb]) and oxygenated hemoglobin concentration ([O₂Hb]) at resting baseline and during the walking test. Upon walking test completion, the participant stood in a resting standing position and a thigh rapid inflation cuff (cuff model SC10, D.E. Hokanson, Bellevue, WA) was placed on the thigh ~ 3-4 centimeters proximal to the knee on the limb with the NIRS device. The cuff was inflated to ~ 250- 260 mmHg for 5 min to deoxygenate the tissue with the same rapid inflation cuff system used for FMD (22, 25). The cuff pressure was released after 5 min, and the peak hyperemic response following cuff release was used to determine the 100% oxygenation level for each participant and was used to calculate normalized [HHb] (22, 25). The raw NIRS data were reduced to 1 Hz files and exported to Microsoft Excel files for later analysis.

Autonomic function

Autonomic nervous system function was measured using heart rate variability. Participants wore a simple heart rate monitor (Suunto Smart Sensor, Suunto, Vantaa, Finland). The researcher assisted the participant with putting on the heart rate monitor. The participant was positioned in a supine position on a padded examination table for 5 minutes. The subject was then be assisted with standing upright in front of the table for 5 minutes. Heart rate was recorded during supine and standing positions and used to determine autonomic nervous activity.

Statistical analysis

The Shapiro-Wilk test was used for all dependent variables to determine the normality of the data. Independent *t*-tests were used to determine any differences between subject characteristics at the MitoQ and PL visits. A two-way repeated measures analysis of variance³ (ANOVA) [group (MitoQ and PL) x time (before and after supplement intake)] was used to compare the changes between MitoQ and PL intake within and between groups on the dependent variables. When a significant main effect or interaction was found, paired *t*-tests were used for *post-hoc* comparisons for the normally distributed variables, and paired samples

3

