Wilcoxon tests were used for non-normally distributed variables. Based on a power calculation from a previous study, a sample size of a minimum of total 14 (n = 7 per group) would allow for 80% power to detect differences between FMD between MitoQ vs. PL (26). Associations between dependent variables were assessed using Pearson's product-moment correlation coefficient. Effect size analyses were conducted using Cohen's *d* and interpreted as 0.2 as a small effect size, 0.5 as a medium effect size, and 0.8 as a large effect size (22, 27). All analyses were performed using SPSS 26.0 (IBM, Armonk, NY). Descriptive characteristics are presented as Mean \pm SD, and all other data are presented as Mean \pm SE. Statistical significance was set to *p* < 0.05.

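### The group × time test fixes the pre-dose slope at 1; a baseline-adjusted analysis of the same four values would often be more precise with 13 participants (optional improvement, not an error)

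*Combined protocol and SAP*

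**What the plan says.** The Design section describes a two-visit crossover: "This study used a randomized, double-blinded, placebo-controlled, crossover design with a washout period of 14 days between the 2 study visits". Every outcome is measured before dosing at each visit ("baseline experimental measurements were conducted, after which the MitoQ supplement or PL were consumed") and again afterwards: "All experimental measurements were repeated ~ 1 h following ingestion". Each participant therefore gives four values per outcome. The Participants section reports "Patients with PAD (n = 13, 7 males and 6 females) were recruited for study participation".

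The Statistical analysis section compares treatments with a two-way repeated measures ANOVA, "group (MitoQ and PL) x time (before and after supplement intake)] was used to compare the changes between MitoQ and PL intake". Follow-up tests depend on it: "When a significant main effect or interaction was found, paired *t*-tests were used for *post-hoc* comparisons for the normally distributed variables", with Wilcoxon tests for variables that are not normally distributed. No section uses the pre-dose value as a covariate, and no period or sequence term is named. The power statement says that a minimum total of 14 "would allow for 80% power to detect differences between FMD between MitoQ vs. PL". It gives no effect size, SD or correlation.

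**The concern.** The pre-dose and post-dose values are separate recordings, each with its own measurement error and within-day variation. The post-dose difference between visits will then usually follow the pre-dose difference with a slope below 1. An analysis that subtracts the whole pre-dose difference adds pre-dose noise to the treatment contrast. When the two pre-dose values happen to differ, it also pushes the estimate too far in the opposite direction.

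At stake is the precision available from 13 people for flow-mediated dilation, walking and near-infrared spectroscopy outcomes, using data that the design already collects.

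**Working it through.** **Inputs.** From the documents: n = 13, four values per participant, the group × time ANOVA, and significance at p < 0.05 (two-sided assumed). Not in the documents, so assumed:
- ρ, the correlation between D_pre = MitoQ pre − placebo pre and D_post = MitoQ post − placebo post;
- k = SD(D_post)/SD(D_pre).

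**The plan's own figure.** The minimum of 14 cannot be reproduced, because no effect size, SD or correlation is given. Solving backwards for 80% power, two independent groups of 7 need a standardised difference of 1.50 (normal approximation) or 1.63 (noncentral t). Paired data need 0.81 SD of the paired differences at n = 14, or 0.85 at n = 13. None of these fixes ρ.

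**Step 1: what the interaction is.** In a 2 × 2 within-person layout, the interaction F is the square of the one-sample t on D_post − D_pre. In a check dataset of 13, the interaction F was 0.6063 and the squared t was 0.6063. The slope on D_pre is therefore fixed at 1. The group main effect is different: its F (0.2758) equals the squared t on the pre + post sums. It is not a change score, yet it too can trigger post-hoc tests.

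**Step 2: variance.** With k = 1 and common SD s:
- planned contrast: 2(1 − ρ)s²/n;
- ignoring the pre-dose values: s²/n, so the planned test does worse than this when ρ < 0.5;
- adjusted, large sample: (1 − ρ²)s²/n, which is (1 + ρ)/2 of the planned variance.

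Estimating the slope at n = 13 multiplies the adjusted variance by 1 + 1/(n − 3) = 1.10, or by 1 + 1/(n − 4) = 1.111 with a sequence term and near-equal sequences. The t quantile rises from 2.179 (12 df) to 2.201 (11 df) or 2.228 (10 df).

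**Step 3: break-even, k = 1.** On variance, 1.10(1 + ρ)/2 = 1 gives ρ = 0.82. Counting the wider t quantile, 1.10 × (2.201/2.179)² × (1 + ρ)/2 = 1 gives 0.78. With a sequence term in the adjusted model only, 1.111 × (2.228/2.179)² × (1 + ρ)/2 = 1 gives 0.72. If both tests carry that term it is 0.76.

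**Step 4: size at n = 13, k = 1.** Rows 1 and 2 are simulated (40,000 runs per ρ, no sequence term). Row 3 is √((1 + ρ)/2) × √1.111 × 2.228/2.179.

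| ρ | 0.2 | 0.4 | 0.6 | 0.8 | 0.9 |
|---|---|---|---|---|---|
| Adjusted power where planned power is 60% | 77% | 71% | 65% | 60% | 58% |
| CI width, adjusted/planned | 0.82 | 0.88 | 0.94 | 1.00 | 1.03 |
| CI width with sequence term (formula) | 0.83 | 0.90 | 0.96 | 1.02 | 1.05 |

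Type I error was 4.9–5.2% for both tests.

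**Step 5: unequal SDs.** The variance ratio is k²(1 − ρ²)/(1 + k² − 2kρ) × 1.10.
- k = 1.1, ρ = 0.7: 1.21 × 0.51/0.67 × 1.10 = 1.01.
- k = 1.2, ρ = 0.6: 1.44 × 0.64/1.00 × 1.10 = 1.01.
- k = 1.2, ρ = 0.8: 1.44 × 0.36/0.52 × 1.10 = 1.10. The CI is √1.097 × 2.201/2.179 = 1.06 times as wide, or √(0.997 × 1.111) × 2.228/2.179 = 1.08 with the sequence term.

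The least-squares slope cannot do worse than a slope of 1 except through the estimation factor, so the variance loss is capped at about 10% (about 11% with the sequence term).

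**Step 6: chance imbalance.** Given an observed pre-dose difference δ, the change-score estimate moves by −(1 − ρ)δ. The adjusted estimate does not move. One standard error of the mean pre-dose difference is 1/√13 = 0.28 SD, so the shift is 0.8 × 0.28 = 0.22 SD at ρ = 0.2 and 0.4 × 0.28 = 0.11 SD at ρ = 0.6.

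**Step 7: which correlation.** If every cross-visit correlation equals r_b and the within-visit correlation is r_w, then ρ = (r_w − r_b)/(1 − r_b). With r_b = 0.5, a within-visit correlation of 0.8 gives ρ = 0.3/0.5 = 0.6. The structure can also work the other way. With r_w = 0.78, a same-time cross-visit correlation of 0.7 and a pre-to-post cross-visit correlation of 0.5, ρ = 0.28/0.30 = 0.93, and the variance ratio is 1.06 against adjustment.

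**The case against.** The strongest reply is that nothing here is wrong. Comparing changes is what the plan sets out to do. Under randomisation the change score is unbiased on average, and its test holds its level. A reader might infer from the imbalance argument that the planned estimate is biased. The documents do not support that: the shift in Step 6 is conditional on a chance difference and averages to zero.

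A reader might also infer that adjustment wins for any within-visit correlation below 0.8. That does not follow either. The governing quantity is the correlation of the between-visit differences, and the threshold needs similar SDs.

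Nor can a definite power loss be claimed. Fasted readings at a fixed hour, about 1 h apart on the same equipment, could share a day effect that raises ρ, and at ρ of 0.6 to 0.8 the gain is 5 points down to none.

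Two practical objections also stand. A change score cancels any visit-level shift common to both readings, whereas a slope below 1 does so only in part. Thirteen people cannot be split into equal sequences, so the adjusted model needs a sequence term. And the document is written in the past tense with recruitment reported. Replacing the planned test after results are known would be a post hoc switch.

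What survives is that no baseline adjustment is planned although the data allow it, the possible gain is sizeable at low to moderate ρ, and the possible loss is small and bounded.

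**Conclusion.** This is an optional, cheap efficiency improvement. The algebra and the absence of a baseline-adjusted analysis are certain. The size is conditional on ρ and k, which the documents do not give. Under equal SDs the gain runs from about 17 power points at ρ = 0.2 (60% to 77%) to none at 0.8, with a loss of about 2 points at 0.9. If the post-dose SD is 1.2 times the pre-dose SD, the advantage ends near ρ = 0.6. The sequence term brings the equal-SD break-even down to about 0.72 against the planned 12-df test. The calculations assume normal data. They do not cover the outcomes that the plan sends to Wilcoxon tests.

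**What to change.** For each outcome, use one row per participant. Regress the post-dose MitoQ-minus-placebo difference on the pre-dose MitoQ-minus-placebo difference, entered uncentred, with sequence coded +1/−1 to remove any period effect. Report the intercept with its 95% CI and p-value as the MitoQ effect at zero pre-dose difference. Report the planned 2 × 2 interaction beside it.

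State in the plan whether outcome data had been analysed when this was added. If they had, label the adjusted result supplementary and post hoc, and do not let it replace the planned test. For non-normal outcomes, leave the planned Wilcoxon tests in place.

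Cost: a few lines of SAP text and one regression per outcome in the SPSS version already named, with no new data. It uses one degree of freedom for the slope and one for sequence. Without the sequence term, the CI is about 3% wider at ρ = 0.9 with equal SDs, and up to about 6% wider if the post-dose SD is 1.2 times the pre-dose SD. With the sequence term these become about 5% and 8%.

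### A time effect shared with placebo can open the post-hoc tests, and no rule ties a MitoQ conclusion to a direct MitoQ-versus-placebo contrast

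*Combined protocol and SAP*

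**What the plan says.** The Design section describes a "randomized, double-blinded, placebo-controlled, crossover design", so each participant has a MitoQ visit and a placebo visit. At both visits there is a baseline set of measurements, then the capsule, and then: "All experimental measurements were repeated ~ 1 h following ingestion".

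The Statistical analysis section specifies a two-way repeated-measures ANOVA with factors "group (MitoQ and PL) x time (before and after supplement intake". The model "was used to compare the changes between MitoQ and PL intake within and between groups on the dependent variables". Post-hoc comparisons follow "When a significant main effect or interaction was found". They are paired t-tests for normally distributed variables; otherwise paired "Wilcoxon tests were used for non-normally distributed variables".

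The sample-size sentence in the same section states that the planned number "would allow for 80% power to detect differences between FMD between MitoQ vs. PL".

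The section does not list the post-hoc pairs. It also does not say which ANOVA effect or which pair decides whether MitoQ worked.

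**The concern.** In this model the main effects are condition (called group in the plan) and time. A significant time effect says only that values changed from before to after, averaged over MitoQ and placebo. It carries no information about MitoQ, yet under the stated rule it is enough to open the paired tests.

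A shared change is plausible. The whole battery, including a treadmill walk to the limit of tolerance, is repeated about an hour later at both visits, so practice, fatigue or warm-up could move both conditions. The documents do not give the size or direction of any such change.

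If the paired tests include before versus after within each condition, chance alone will often make one significant and the other not. Reading that as a treatment effect would report benefit if the shared change is an improvement, or harm if it is a decline. The mirror result, significant on placebo only, is equally likely and would mislead the other way. The placebo visit exists to remove such shared changes, and this route bypasses it.

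Two other comparisons are not at fault. With randomised order and no carry-over, the condition main effect and the MitoQ-after versus placebo-after pair are valid MitoQ-versus-placebo comparisons. The condition effect is diluted because it averages in the pre-capsule values.

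**Working it through.** **The plan's own figure.** The minimum of 14 participants for 80% power cannot be reproduced, because no effect size or SD is given. Back-solving gives a standardised difference of 1.63 for two independent groups of 7, or 0.81 for 14 pairs. Nothing below depends on this.

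**Inputs from the documents.** n = 13 (Participants); significance at p < 0.05 (Statistical analysis; two-sided assumed, as sidedness is not stated); the rule for opening post-hoc tests (Statistical analysis).

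**Assumptions, not in the documents.**
- There is no MitoQ effect.
- The mean before/after change is the same in both conditions, between 0 and 1.0 SD of the change score, with normal data.
- The correlation between a person's two changes is 0, 0.3, 0.5 or 0.8.
- Within-condition pairs are tested.

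**Reduction to paired tests.** Let D_M and D_P be one person's after-minus-before changes on MitoQ and placebo. In a 2 × 2 within-person ANOVA:
- time effect: t-test on (D_M + D_P)/2
- interaction: t-test on D_M − D_P
- condition effect: t-test on the difference between the two visit means

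Each uses t = mean/(SD/√13), with critical value 2.179 on 12 df.

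**Simulation, 100,000 trials per setting.** Post-hoc tests open if time, condition or interaction has p < 0.05; D_M and D_P are then each tested against zero. Entries are percent of outcomes at correlation 0 / 0.8, counting significance in either direction.

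| Shared change (SD) | MitoQ significant, placebo not | Placebo significant, MitoQ not | First pattern, opened by time alone |
|---|---|---|---|
| 0 | 2.8 / 1.8 | 2.7 / 1.8 | 1.2 / 1.2 |
| 0.2 | 6.2 / 3.1 | 6.2 / 3.1 | 4.2 / 2.3 |
| 0.3 | 10.7 / 4.5 | 10.8 / 4.5 | 8.0 / 3.4 |
| 0.5 | 20.8 / 7.5 | 20.8 / 7.3 | 17.4 / 5.8 |
| 0.6 | 23.1 / 8.1 | 22.8 / 8.2 | 19.7 / 6.4 |
| 0.8 | 18.1 / 6.6 | 18.1 / 6.6 | 15.4 / 5.2 |
| 1.0 | 8.1 / 3.5 | 8.1 / 3.4 | 6.6 / 2.8 |

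Adding a visit effect with SD 0.5 (tried at 0, 0.5 and 0.6 SD) moves the MitoQ-only column by at most 0.3 points.

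**Hand check at correlation 0.** Each within-condition test has power 38% at 0.5 SD and 51% at 0.6 SD. Without any opening rule, the chance that MitoQ is significant and placebo is not would be 0.38 × 0.62 = 23.6% and 0.51 × 0.49 = 25.0%. The plan's rule lowers these only to 20.8% and 23.1%.

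**Which effect opens the tests.** At 0.5–0.6 SD the time effect alone accounts for 77–85% of the MitoQ-only results. For example, at 0.6 SD and correlation 0, 19.7/23.1 = 85%; at 0.5 SD and correlation 0.8, 5.8/7.5 = 77%. The condition effect alone opens at most 0.2% in any setting.

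**Other opening rules, same settings.** Dropping the time effect brings the MitoQ-only rate to 0.6–3.4%. Opening on the interaction alone gives 0.4–2.3%.

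**Direct contrasts.** With no MitoQ effect, the interaction, the condition effect and the after-versus-after pair each reject in 4.8–5.1%.

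**Narrower count.** Leaving the condition effect out of the rule and counting improvement only, the MitoQ-only rate at correlation 0.5 to 0 is 13–21% at 0.5 SD and 14–23% at 0.6 SD.

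**The case against.** The strongest reply is that the right contrast is already in the plan. Comparing the changes between MitoQ and placebo is the interaction, and the plan gives that comparison as a purpose of the ANOVA. This is correct: the direct contrast is computed. What is absent is a rule that it decides, and the same sentence puts within-condition comparisons beside it on an equal footing.

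A second reply is that the harm needs three things the documents do not establish: that within-condition pairs are tested, that a MitoQ claim is drawn from one being significant and the other not, and that a moderate shared change exists. This stands as a limit on the size of the problem. With a shared change of 0–0.2 SD the misleading pattern occurs in only 2–6% of outcomes. Rates above 20% need a shared change near 0.5–0.6 SD and almost no correlation between a person's two changes. The plan permits this route; it does not state that it would be taken.

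A third reply is that choosing the interaction over the after-versus-after pair is partly preference. That is fair as to power, and the cost is set out with the fix. It does not defend letting a time effect open the tests.

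Finally, the document is dated July 2023, is written in the past tense and reports 13 participants already recruited. A rule added now may not count as pre-specification. That affects how the change is described, not whether it is needed.

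**Conclusion.** The concern holds and should be fixed; confidence is medium. That the time effect opens the post-hoc tests, and that no deciding contrast is named, follows directly from the Statistical analysis section. The size of the harm is conditional. If within-condition tests are run and read as treatment evidence, a false MitoQ-only result appears in about 2–3% of outcomes with no shared change. It rises to at most 23% on the assumed grid and falls back to 3–8% at 1.0 SD. The 23% is the top of an assumed range, not an estimate for this trial.

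**What to change.** In the Statistical analysis section and in the results:
- State that MitoQ conclusions rest on the interaction the plan already computes, that is, the within-person difference in change between MitoQ and placebo. Report it with its 95% CI for every outcome.
- Do not let a time main effect alone open post-hoc tests that support a MitoQ claim.
- List the post-hoc pairs, and label before/after tests within a condition as descriptive.
- Where within-person differences are clearly non-normal, apply the Wilcoxon signed-rank test to the difference in change.
- Say when the rule was adopted.

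The cost is a few sentences and re-reporting from existing data, with no new measurements. Fewer results may be called significant. With 13 participants, 80% power is reached only for a difference in change of about 0.85 SD of the within-person difference, and the 95% CI half-width is about 2.179/√13 = 0.60 SD.

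The interaction is not always the most powerful valid contrast. For a MitoQ effect of 0.8 SD of a visit-level value, its power is 35%, 47% and 68% at before/after correlations of 0.3, 0.5 and 0.7, against 46–47% for after-versus-after. The last figure assumes no correlation between the two visits' after-values (0.8/√2 = 0.57 SD of the difference). If the 0.8 is in units of total SD and that correlation is 0.5, the difference is 0.8/√(2 × 0.5) = 0.8 SD and the power is 75%. The documents give neither correlation, so these figures show only what the choice may cost.

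### The 80% power for FMD is stated for at least 14 (7 per group), but 13 were recruited to a crossover, so the figure is not established for the trial as run

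*Combined protocol and SAP*

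**What the plan says.** The only power statement is in the Statistical analysis section. It relies on a calculation from a previous study and says that "a sample size of a minimum of total 14 (n = 7 per group) would allow for 80% power to detect differences" in FMD between MitoQ and placebo. It gives no FMD difference, SD, within-person correlation or sidedness.

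Three other places bear on it:

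- Participants: "Patients with PAD (n = 13, 7 males and 6 females) were recruited for study participation".
- Design: "This study used a randomized, double-blinded, placebo-controlled, crossover design with a washout period of 14 days between the 2 study visits".
- Statistical analysis, describing the repeated-measures ANOVA: "group (MitoQ and PL) x time (before and after supplement intake". Here the two groups are the two conditions.

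The power statement does not name the artery, although the Endothelial function section says "Endothelial function was assessed using brachial artery flow-mediated dilation (FMD) and popliteal artery FMD". On reporting, descriptive characteristics are given with SD, while "all other data are presented as Mean" with SE. Cohen's d is planned as an effect size.

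**The concern.** A total sample size normally counts people. Counted that way, the trial has 13 against a stated minimum of 14, and the document does not mention the gap. The per-group number does not help. In a crossover every participant contributes to both conditions, so 13 people give 13 under MitoQ and 13 under placebo, and neither number is 7. The 7 could be a sequence size, the size of an independent group in the earlier study, or a number of people measured under both conditions. The document does not say which.

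This is the document's only power figure. A reader facing a non-significant FMD result cannot tell what difference 13 crossover participants could have detected, or in which artery. Means with SEs for each condition do not by themselves give an interval for the MitoQ–placebo difference, because they leave out the within-person correlation.

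**Working it through.** **Inputs from the document.** 14 in total, 7 per group, 80% power and significance at p < 0.05 (Statistical analysis); 13 recruited (Participants); two-period crossover (Design); condition-by-time ANOVA with paired post-hoc tests (Statistical analysis).

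**Assumptions.** Two-sided testing. The meaning of the 14 is also an assumption, so each reading is taken in turn.

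**Step 1: the plan's own figure.** The 80% cannot be reproduced because no effect, SD or correlation is given. The only sum that can be checked is 2 × 7 = 14, which is right. What can be done is to solve for the standardised effect that makes each reading give exactly 80%, and then find the power of 13 crossover participants at that effect.

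**Step 2: formulas.** With complete data, the condition-by-time interaction is a paired t-test on each person's contrast (change with MitoQ minus change with placebo). With d_z = mean ÷ SD of the contrast, the noncentrality is d_z × √n on n − 1 degrees of freedom. Power comes from the noncentral t distribution.

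**Step 3: 14 means 14 crossover participants.** 80% at n = 14 needs d_z = 0.810. At n = 13 the noncentrality is 0.810 × √13 = 2.92 on 12 df, and power is 76.5%.

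**Step 4: 7 means 7 per sequence, with period adjustment.** This is a two-sample t-test on period differences, with noncentrality 2 × d_z × √(n1 × n2 ÷ (n1 + n2)). 80% at 7/7 needs d_z = 0.816. An assumed 7/6 split then gives 2 × 0.816 × √(42/13) = 2.93 on 11 df, and power is 76.1%.

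**Step 5: 7 means 7 per independent group.** The noncentrality is d × √(7/2) on 12 df, and 80% needs d = 1.632. Suppose d is in SDs of a single measurement and all four measurements share the same variance and correlation ρ. The difference of changes then has variance 4(1 − ρ) in those units, so d_z = 1.632 ÷ √(4(1 − ρ)):

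| ρ | d_z | Power at n = 13 |
|---|---|---|
| 0 | 0.816 | 77.0% |
| 0.07 | 0.846 | 80% |
| 0.3 | 0.975 | 89.7% |
| 0.5 | 1.154 | 96.8% |

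If d was instead on the scale of change scores, or applies to a simple paired comparison, d_z = 1.632 ÷ √(2(1 − ρ)). Power is then 96.8% at ρ = 0 and higher above it.

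**Step 6: 7 means 7 people measured under both conditions.** 80% needs d_z = 1.273. With 13 people and the same contrast, power is 98.7%. If the earlier contrast was a simple paired difference, moving to the difference of changes doubles the variance under the same assumptions. Then d_z = 1.273 ÷ √2 = 0.900 and power is 84.5%.

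**Step 7: what 13 can detect.** Solving for 80% power at n = 13 gives 0.847, or about 0.85 SD of the contrast. It is 0.86 SD if period-adjusted with a 7/6 split. Without period adjustment it is 0.89 at n = 12, 0.94 at 11 and 1.00 at 10. The 95% CI half-width at n = 13 is 2.179 ÷ √13 = 0.60 SD.

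**The case against.** The best defence is that the analysis text itself defines group as condition. Carried to the power statement, that makes 7 per group 7 people under each condition, which 13 in a crossover exceeds. A crossover is also usually more efficient than independent groups, so a figure borrowed from a parallel comparison could be conservative. If the trial is one short, the loss is under 4 percentage points. The missing artery and inputs are missing detail, not a wrong sum, and they may be in the cited study, which is not available here.

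Much of this stands. A reader might infer that the trial is underpowered, or that 80% fails however the sentence is read. The document supports neither: several readings put power well above 80%, and on Step 6 the claim of 80% is comfortably met. No calculation is shown to be wrong.

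The defence does not settle the point, because reading group as condition sits badly with a total of 14: 7 people under each of two conditions are 7 people, not 14. The efficiency argument also depends on the reading and on the correlation. For the difference of changes in Step 5, power is below 80% when ρ is under about 0.07.

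It can also be said that 0.85 SD holds for any 13-person paired comparison and says nothing in FMD units. That is fair, and it is why the confidence interval is needed as well. The 0.85 SD is not post-hoc power in the usual sense, since it uses only n and alpha and no observed result.

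**Conclusion.** The point holds in a limited form. Taken as participants, the stated minimum was missed by one without explanation, and the per-group number does not match the document's own use of group. The 80% is therefore not established for the trial as run.

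If 14 meant crossover participants or 7 per sequence, power at the planning effect is about 76% instead of 80%. On the other readings examined it runs from 77% to 99% or more, and is mostly above 80%. These figures assume two-sided 5% testing, usable FMD data from all 13 in both periods and, where ρ appears, equal variances and correlations. Which reading was intended cannot be decided from the document, so underpowering is not shown.

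**What to change.** 1. Keep the original planning basis on record. Say what the 14 and the 7 per group counted (participants, sequences, independent groups, or people measured under both conditions) and whether the calculation concerned brachial or popliteal FMD.
2. State that 13 were recruited. If 14 meant participants, add that the planned minimum was not reached and that power at the planning effect is about 76%.
3. Replace the 80% claim with one for the actual design, for example: *With 13 participants contributing FMD data in both periods, the study has 80% power (two-sided 0.05) to detect a MitoQ–placebo difference of about 0.85 SD of the within-participant contrast (change with MitoQ minus change with placebo).* Use 0.86 SD if the analysis is period-adjusted with a 7/6 split, and update the figure if fewer have usable data.
4. For each artery, report the 95% CI for the MitoQ–placebo difference in FMD % units alongside the planned Cohen's d.

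The cost is a few sentences and one interval per artery from data already collected. The stated power may look slightly less favourable. No new data, enrolment or change of test is needed.
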